## **1.0 LIST OF ABBREVIATIONS**

ADT	Androgen deprivation therapy
AE	Adverse event
ALT	Alanine aminotransferase
AST	Aspartate aminotransferase
BUN	Blood urea nitrogen
CTX	C-Telopeptide cross-links of type I collagen
eCRF	Electronic Case report form
DHEA	Dehydroepiandrosterone
DHEAS	Dehydroepiandrosterone sulfate
DHT	Dihydrotestosterone
ECOG	Eastern Cooperative Oncology Group
ER	Estrogen receptor
ES	Elastic stockings
FXaI	Factor X inhibitor
GCP	Good clinical practice
GGT	Gamma-glutamyl transferase
hERG	Human ether-à-go-go related gene
IEC	Independent ethics committee
IMP	Investigational medicinal product
IPC	Intermittent pneumatic compression
IRB	Institutional review board
IUD	Intrauterine device
IUS	Intrauterine system
IWRS	Interactive Web Response System
LDH	Lactate dehydrogenase
LDL	Low density lipoprotein
LDUH	Low dose unfractionated heparin
LH	Luteinizing hormone
LHRH	Luteinizing hormone releasing hormone
LMWH	Low molecular weight heparin
MedDRA	Medical dictionary of regulatory activities
MRI	Magnetic resonance imaging

MMRM	Mixed Models Repeated Measures
NSAID	Nonsteroidal anti-inflammatory drug
OTC	Over the Counter
PCWG2	Prostate Cancer Working Group 2
PRN	Pro re nata – As Needed
PSA	Prostate specific antigen
SAE	Serious adverse event
SHBG	Sex hormone binding globulin
SRE	Skeletal related event
T 1/2	Plasma concentration elimination half-life
TNM	Tumor staging, T = primary tumor, N = lymph nodes, M = distant metastases

## **2.0        PROTOCOL SUMMARY**

**Study  
Number:**        V72203

**Title:**            Randomized, double-blind, placebo controlled, dose finding Phase 2 study comparing oral daily dosing of VERU-944 after a week of loading (daily dosing) with placebo to ameliorate the vasomotor symptoms resulting from androgen deprivation therapy in men with advanced prostate cancer

**Primary  
Objective:**        To determine an effective dose of VERU-944 (from among 10 mg, 50 mg, and possibly 100 mg PO q day), after a loading dose, for the treatment of vasomotor symptoms commonly known as hot flashes by assessing its effect on:

1. the frequency of moderate to severe hot flashes at week 6

**Secondary  
Objectives:**        To assess the effect of VERU-944 on:

1. the severity of moderate to severe hot flashes at week 6
2. the frequency of moderate to severe hot flashes at week 8
3. the frequency of moderate to severe hot flashes at week 10
4. the frequency of moderate to severe hot flashes at week 12
5. the severity of moderate to severe hot flashes at week 8
6. the severity of moderate to severe hot flashes at week 10
7. the severity of moderate to severe hot flashes at week 12
8. the frequency of moderate to severe hot flashes at week 4
9. the severity of moderate to severe hot flashes at week 4
10. bone turnover markers

To assess the effect of VERU-944 on:

**Exploratory  
Objectives:**        1. serum PSA concentrations

                          2. serum total and free testosterone concentrations

                          3. serum SHBG concentrations

To assess the safety and tolerability of VERU-944

**Safety  
Objective:**

**Design:** This study is a multicenter, randomized, double-blind, placebo controlled, dose finding study of VERU-944 to treat hot flashes (vasomotor symptoms) in men with advanced prostate cancer on ADT. The study will be conducted as a staged study with Stage 1 being a three-arm evaluation of placebo, 10 mg and 50 mg of VERU-944. When all subjects have completed Week 6 (Day 42) of dosing, an evaluation of the efficacy of the doses administered in Stage 1 will be made (safety will be assessed in a blinded review) and Stage 2, a two-arm evaluation of placebo and 100 mg VERU-944 may be initiated. Stage 1 of the study will have three arms (placebo, 10 mg VERU-944, and 50 mg VERU-944) and Stage 2 of the study will have two arms (placebo and 100 mg VERU-944) with approximately 30 subjects per arm. The subjects participating in the study will have advanced prostate cancer and will be undergoing androgen deprivation therapy (ADT) with a luteinizing hormone releasing hormone (LHRH) therapy (agonist or antagonist) for at least the three months prior to randomization and be experiencing regular moderate to severe hot flashes while on ADT. Subjects will all continue to receive ADT and will be randomized to receive, for the first four days, a loading dose followed by daily doses of placebo or VERU-944 (10 mg, 50 mg or 100 mg) orally for a total period of 12 weeks.

**Subjects:** Approximately, ninety (90) subjects will be randomized into Stage 1 of this study and approximately 60 subjects are planned to be randomized into Stage 2 of this study. Subjects with advanced prostate cancer who have experienced moderate to severe vasomotor symptoms (hot flashes) for at least one month prior to study entry will be enrolled. Subjects must have been maintained on ADT with an LHRH agonist or antagonist for at least the 3 months prior to randomization will be screened for the study and if these subjects meet the other inclusion/exclusion criteria, will be randomized into the study.

**Treatments:** Subjects will be maintained on ADT with an LHRH agonist or antagonist while on the study. In addition to ADT, each subject will be orally administered either placebo, 10, or 50 mg of VERU-944 daily after they have completed a four day loading dose as outlined in [Section 7.3](#) in Stage 1 of the study. Each subject in Stage 2 of the study will receive either placebo or 100 mg of VERU-944 daily after they have completed a four day loading dose as outlined in [Section 7.3](#).

**Procedures:** Potential study participants will undergo a series of screening evaluations within 28 days prior to randomization. Subjects who give written informed consent and satisfy the selection criteria will be enrolled into the study.

The frequency and severity of hot flashes will be recorded daily beginning with screening and through week 12 (Day 84). Assessments of serum total and free testosterone, serum SHBG and serum PSA will be made at baseline (Day 1), Days 30, 60 and 84. Bone turnover markers will be assessed at baseline (Day 1) and Day 84.

Safety evaluations including assessment of adverse events, serum PSA, periodic monitoring of vital signs, 12-lead electrocardiogram (single) and clinical laboratory results (including hematology, serum chemistry (including LDH) will be conducted at every visit.

Patients that have been previously screened for this study and could not complete screening for reasons other than not meeting the inclusion and exclusion criteria, may be rescreened into the study. Laboratory testing conducted under this protocol ([Appendix A](#)) within 45 days prior to randomization into this study, may be used as the baseline laboratory values for this study and repeat laboratory testing is not required unless new coadministered medication(s) has been started, unless the investigator determines that retesting is warranted.

**Stage 2  
dosing  
evaluation:**

After the last subject has completed Day 42 of Stage 1, an unblinded assessment of the Week 6 (Day 42) hot flashes frequency (primary endpoint), hot flash severity (first secondary endpoint), and a blinded assessment of safety of VERU-944 will be conducted.

If an effective dose of VERU-944 has been identified in Stage 1, Sponsor reserves the right to not initiate Stage 2 of this protocol.

If an unacceptable safety profile is observed in Stage 1, Sponsor reserves the right to not initiate Stage 2 of this protocol.

### **3.0 INTRODUCTION**

#### **3.1 Background**

Veru Inc. is developing VERU-944 (cis-clomiphene), a nonsteroidal estrogen, as a hormonal therapy for the alleviation of vasomotor symptoms, commonly known as hot flashes in men undergoing ADT. Cis-clomiphene is one of two geometric isomers of clomiphene, which is approved as Clomid® (clomiphene citrate oral capsules, 50 mg; NDA 016131; Sanofi Aventis US) for the treatment of ovulatory dysfunction in women desiring pregnancy. While trans-clomiphene is anti-estrogenic, cis-clomiphene is an estrogen agonist at pharmacologic concentrations (Turner et al., 1998; Fitzpatrick et al., 1999; Kaminetsky et al., 2013). Furthermore, cis-clomiphene has a half-life of 5–7 days (Mikkelsen et al., 1986; Mürdter et al., 2012). VERU-944 is expected to be effective and safe in men with prostate cancer undergoing ADT based on the established efficacy of low dose estrogens in the treatment of vasomotor symptoms (hot flashes) and safety of off-label clomiphene use for male infertility.

#### **3.2 Target Indication and Pharmacologic Activity**

##### Introduction

Prostate cancer is the most common cancer in men with over 160,000 new cases expected in 2017 (American Cancer Society. Cancer Facts & Figures 2017). As advanced prostate cancer is hormone sensitive, androgen deprivation therapy (ADT) is the standard of care for patients with metastatic or locally advanced prostate cancer, either alone or in combination with other drug treatments or radiation (National Comprehensive Cancer Network, 2016). The main objective of ADT is to lower the serum testosterone level to castrate level of approximately 1.7 nmol/L (< 50 ng/dL) (Djavan et al., 2012). ADT is usually achieved either by surgical orchiectomy (castration) or by medically administering LHRH (luteinizing hormone releasing hormone) agonists and antagonists.

One of the main side effects of low testosterone levels in men is vasomotor symptoms, commonly known as hot flashes. Hot flashes are experienced by about 75% of men receiving ADT (Holzbeierlein et al., 2004) and are a significant component in men's perception of their quality of life (Holzbeierlein et al., 2004). One study found 38% of men who had experienced hot flashes over the past four weeks were distressed about them (Holzbeierlein et al., 2004). These hot flashes can have a long duration. For example, in men experiencing hot flashes while on ADT, 70% of them continued to experience them five years later (Karling 1994). Men describe their experience of hot flashes with physical as well as emotional descriptors (Isbarn et al., 2008). Up to 80% of men have described hot flashes that range from mild to very severe, lasting up to 30 minutes and accompanied by feelings of anxiety, irritability and being out of control. (Schow 1998). Hot flashes for men, as for women, often require some sort of action such as changing clothes or taking a shower (Isbarn et al., 2008). Hot flashes in men who have advanced prostate cancer being treated by ADT have detrimental effects on overall quality of life such that cancer-related distress caused by hot flashes are a contributing factor in the discontinuation of ADT (Engstrom, 2008; Ulloa et al., 2009; Frisk, 2010).

The precise mechanism of hot flashes in men is not fully understood, but appears to be similar to postmenopausal hot flashes in women. Studies in postmenopausal women and women undergoing breast cancer treatment who experience hot flashes have shown that abrupt withdrawal of sex hormones leads to a dysfunctional hypothalamic thermoregulation resulting in vasomotor flushing (Kaplan and Mahon, 2014). In women, hormones (usually estrogen combined with progesterone), selective serotonin reuptake inhibitors (SSRIs) and serotonin-noradrenalin reuptake inhibitors (SNRIs), clonidine, and gabapentin have been effective in treating hot flashes. Similar treatments have been attempted in men with inconsistent activity; overall, hormonal treatments (cyproterone and medroxyprogesterone) are generally thought to be more effective than non-hormonal treatments at reducing hot flashes in men on ADT (Loprinzi et al., 1994; Frisk, 2010; Irani et al., 2010; Vitolins et al., 2013). Hot flashes in men on ADT are typically treated by off-label treatments such as an SSRI, whereas hormones such as estrogen and megestrol are reserved for refractory cases (Smith and Crawford, 2017).

### Hot Flash Treatment for Men

There are no approved therapies for the treatment of moderate to severe vasomotor symptoms in men with advanced prostate cancer on ADT. There have been few placebo controlled, multicenter studies evaluating possible drug interventions for hot flashes these men. Megestrol acetate, 20 mg twice a day (Loprinzi et al., 1994), depomedroxyprogesterone 400 mg IM (Brosman S 1995), and venlafaxine 12.5 mg twice a day has been investigated as a tool to address hot flashes in men (Loprinzi et al., 1999). A very small randomized trial was completed with 12 men after orchiectomy with cyproterone acetate (100 mg three times a day) which appeared to reduce hot flashes (Eaton and McGuire, 1993). In addition to hormonal approaches, in women, the norepinephrine reuptake inhibitor, venlafaxine, has been studied and shown to be an effective non-hormonal treatment for hot flashes (Evans et al., 2005) although there is no evidence that this approach will work in men.

Another drug that has received some pilot testing, specifically in men, is sertraline as reported in a series of case studies (Roth and Scher 1997). Five men who were being treated with androgen ablation therapy for prostate cancer exhibited symptoms of hot flashes, symptom distress, trouble sleeping, worsening mood, fatigue and illness concerns. Patients were treated with sertraline, starting with 25 mg daily, and titrated up to 100 or 150 mg daily. From these five cases, it appeared that improvement in hot flashes was not experienced until the dose was at least 50 mg daily and side effects were experienced at a dose of 150 mg daily. Specific reductions in hot flashes were not provided for every case, but one man experienced a 75 % reduction in hot flashes while another experienced a 50% reduction. In addition to hot flash reduction, the author reports improvement in mood and irritability (Roth and Scher 1997). Doses from 50 mg to 100 mg appeared to be tolerated very well in this small group of cases.

### **Gabapentin for the treatment of hot flashes**

To date, there has only been one placebo-controlled, Phase 3 study of an agent to control hot flashes in men with prostate cancer on ADT. This study, albeit non-regulatory, investigated the anti-seizure medication, gabapentin. In this trial, men with bothersome hot flashes as

defined as the occurrence of at least 14 times per week, were evaluated and of sufficient severity to make the patient desire therapeutic intervention, with the hot flashes being present for at least 1 month before study entry. The study duration was four weeks and during this time, the patients on the highest gabapentin dose arm (900 mg/day) demonstrated a significant decrease in hot flash frequency ( $p=0.02$ ) and a trend towards lower scores ( $p=0.10$ ) (Loprinzi 2009). In a continuation phase of this study, those effects were maintained (Moraska et al., 2007). Although these results were promising, gabapentin is not widely used for the treatment of hot flashes in this male population and the unmet medical need remains.

### **Estrogens for the treatment of hot flashes in men with advanced prostate cancer on ADT**

As stated briefly above, vasomotor symptoms (hot flashes) occur in a majority of men receiving ADT for advanced prostate cancer. Since decreasing estrogen levels as a result of the ADT are a contributing cause of the hot flashes, the off-label use of estrogenic compounds have historically been used. For example, low doses of diethylstilbestrol (0.25 mg/day) appears to have efficacy but can result in significant breast swelling and tenderness along with an increase in cardiovascular side effects (Smith JA 1994; Smith JA 1996; Glashan 1981). Transdermal estrogen patches are another route of off-label administration of estrogens for this indication. In a study of twelve men with moderate to severe hot flashes who were randomized to receive either low dose (0.05 mg) or high dose (0.10 mg) estrogen twice weekly for four weeks. Although no placebo group was included in this study, a significant reduction in the severity and frequency of hot flashes was observed in the high dose arm and in severity only in the low dose arm (Gerber 2000).

In conclusion, while the off-label use of estrogens appears to have benefit for the treatment of hot flashes in men with advanced prostate cancer, the type of most efficacious estrogen or estrogen preparation as well as dosing route or schedule is not known. Furthermore, the potential for safety issues with potent steroidal estrogens remains a significant limitation to their clinical utility. These published data support the evaluation of VERU-944 to determine the optimal dose for efficacy and safety of a nonsteroidal estrogen to treat hot flashes in men with advanced prostate cancer on ADT.

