### **6.2.2 Exclusion Criteria**

Any of the following conditions are cause for exclusion from the study:

1. Have a serum total testosterone concentration > 50 ng/dL at screening
2. Known hypersensitivity or allergy to estrogen or estrogen like drugs
3. Any disease or condition (medical or surgical) which might compromise the hematologic, cardiovascular, endocrine, pulmonary, renal, gastrointestinal, hepatic, or central nervous system; or other conditions that may interfere with the absorption, distribution, metabolism or excretion of study drug, or would place the subject at increased risk
4. Subjects with a personal history of abnormal blood clotting or thrombotic disease, including venous or arterial thrombotic events such as a history of stroke, deep vein thrombosis (DVT), and/or pulmonary embolus (PE)
5. Any subjects, as determined by a central laboratory, that have a:
  - Factor V Leiden gene mutation
  - Prothrombin gene mutation
6. Uncontrolled symptomatic congestive heart failure (NYHA Class III – IV), unstable angina pectoris, cardiac arrhythmia, or uncontrolled atrial fibrillation
7. History of MI in the past 12 months
8. The presence of consistently abnormal laboratory values which are considered clinically significant. In addition, any subject with liver enzymes (ALT or AST) above 2 times the upper limit of normal, total bilirubin above 2 times the upper limit of normal, or serum creatinine above 1.5 times the upper limit of normal will NOT be admitted to the study
9. Received an investigational drug within a period of 90 days prior to enrollment in the study
10. Received the study medication (VERU-944) previously
11. Have previously taken within 3 months prior to screening or are currently taking diethylstilbestrol, other estrogens;

12. Currently taking gabapentin, estrogen, diethylstilbestrol, medroxyprogesterone acetate, clomiphene, selective serotonin reuptake inhibitors (SSRIs), other treatments for hot flashes
13. Recent hospitalization for more than 24 hours (within 30 days of screening)
14. Recent surgery (within 30 days of screening)
15. Have been previously diagnosed or treated for active cancer (other than prostate cancer or non-melanoma skin cancer) within the previous five years
16. Have a BMI >40
  
17. Have been randomized into Stage 1 of this protocol

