### **8.13.4 Initial Reports**

SAEs will be collected from the time of first study drug administration through 30 days after receipt of final dose of study drug. SAEs and events of clinical interest must be reported to the Sponsor (or designee) within 24 hours of the knowledge of the occurrence.

In the event an SAE is observed or reported, the SAE report will be completed as thoroughly as possible including all available details about the event and the signature of the Investigator. If the Investigator does not have all information about an SAE, the Investigator will not wait to receive additional information before notifying the Sponsor of the event and completing the form. The form will be updated when additional information is received.

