### **9.3.4 Safety Analysis**

The frequency of adverse events (AEs) will be tabulated by MedDRA term and system organ class. The incidence of AEs and the maximum intensity and frequency of AEs will be summarized. A new onset AE is defined as an AE that was not present prior to treatment with study medication but appeared following treatment, or was present at treatment initiation but worsened during treatment. An AE that was present at treatment initiation but resolved and then reappeared while the patient was on treatment is a new-onset AE (regardless of the intensity of the AE when the treatment was initiated).

All laboratory results, vital sign measurements, and other safety variables will be summarized using appropriate descriptive statistics. Changes from baseline will be computed and will be summarized using appropriate descriptive statistics.

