## 6.4 Safety Analysis

## 6.4.1 Adverse Events

A treatment-emergent adverse event (TEAE) is defined as any event not present before the date of treatment with the first dose of study drug, or any event already present that worsens in severity on or after the date of the first dose of study drug.

The calendar date is to be collected for the start and stop of each AE. In the event that only a partial end date (month/year) is available, and the month/year occurs before Day 1 in the treatment period of the study, the AE will not be considered treatment-emergent. However, if the onset date is a partial date (month/year) and the month/year occurs on or after Day 1 in the treatment period of the study, the following cases will be considered:

- The AE will be considered as treatment-emergent if:
  - The month/year of the onset date is later than the month/year of Day 1 in the treatment period.
  - The month/year of the onset date is equal to the month/year of Day 1 in the treatment period of study, and the AE is ongoing at the end of study or the end date and time are present in full or are partially provided such that they place the stop of the AE after the start of exposure to study treatment on Day 1 in the treatment period of the study.

Otherwise, the AE will be considered to be not treatment-emergent and will not be summarized; however, it will be included in the listing.

AEs will be summarized based on subjects having at least 1 occurrence of the AE at the level of the MedDRA preferred term, with the subject as the unit of analysis. If a subject has more than 1 AE of the same preferred term and there are different grades of severity, only the highest grade will be represented in the summary of severity. If the severity assessment is missing, the severity will be reported as 'unknown', and the known severity will be reported over the unknown severity. Each AE will be assessed for relatedness to the study treatment. If a subject has more than 1 AE of the same preferred term and there are different levels of relatedness to study treatment, only the highest level of relatedness for each will be represented in the summary of relatedness. Missing relationships will be included as related.

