The following summaries of TEAEs by system organ class (SOC) and preferred term (PT) for the safety population will be provided. Summaries will be displayed by number of subjects with the event, percentage of subjects with the event and number of events reported by treatment group and overall for the following groups:

- TEAEs
- Serious adverse events (SAEs)

Similarly, summaries will also be displayed by number and percentage of subjects with the event reported by treatment group and overall for the following groups:

- TEAEs by maximum severity and incidence
- TEAEs by strongest relationship to study treatment number and incidence

Any adverse events, serious adverse events, actions taken due to adverse events, discontinuation from the study due to adverse events, adverse event outcomes, and adverse events resulting in study discontinuation will be listed.

Summary tables and listings will be presented by treatment group for the safety population.

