## 6.8 Data Monitoring Committee

There will be no formal Data Monitoring Committee for this study. Safety data, including all SAEs, will be reviewed on an ongoing basis by a Safety Review Team comprised of the Medical Monitor, and representatives of the Sponsor. This Safety Review Team will meet at least monthly. Additional ad hoc meetings will be scheduled if required to evaluate the safety and/or thromboembolic events further

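### The SAP plans no grouped by-arm count of men with any thromboembolic or ischaemic event, or any breast event, and the preferred-term rows it does plan cannot be added to give one

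*Protocol*

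**What the plan says.** **The harms in view.** Protocol 3.2, on estrogens for hot flashes, says that low-dose diethylstilbestrol "can result in significant breast swelling and tenderness along with an increase in cardiovascular side effects". Thrombosis is handled elsewhere. Protocol 6.2.2 item 4 excludes "Subjects with a personal history of abnormal blood clotting or thrombotic disease". Protocol 8.2 requires a thrombophilia panel and a Doppler examination at screening. Protocol 8.10 sets rules for men whose thrombosis risk rises during the study. Appendix B schedules the Caprini assessment at five time points. Protocol 9.3.4.1 and SAP 6.8 both describe the Safety Review Team; in the SAP's words, "Additional ad hoc meetings will be scheduled if required to evaluate the safety and/or thromboembolic events further".

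**The planned tables.** Protocol 9.3.4 says that the frequency of adverse events "will be tabulated by MedDRA term and system organ class". SAP 6.4.1 sets the unit: "AEs will be summarized based on subjects having at least 1 occurrence of the AE at the level of the MedDRA preferred term". It then states: "The following summaries of TEAEs by system organ class (SOC) and preferred term (PT) for the safety population will be provided". These tables give subjects, percentages and numbers of events by treatment group and overall, for treatment-emergent events and for serious events. There are also by-arm tables by maximum severity and by strongest relationship to treatment.

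**The only thrombosis-specific output.** SAP 6.6 summarises the Caprini assessment by visit and arm. That is a risk score, not a count of events.

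**The concern.** The trial spends considerable effort on anticipating thrombosis, and the protocol cites breast and cardiovascular effects as the known cost of an older estrogen. One would therefore expect the analysis to say how many men in each arm had any event of each kind. It does not. Events of one kind are spread over several preferred terms, and with about 30 men per arm most of those rows will hold very small counts.

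What is at stake is how readable the final safety comparison is. If related events fall one or two to a row, an excess on one dose can look like isolated cases. A group of terms assembled after unblinding is open to the challenge that the terms were chosen to fit the result.

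**Working it through.** The plan states no figure for this point, so there is nothing to reproduce. The check has three steps.

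**1. Is a grouped count planned anywhere?** I read Protocol 9.3.4 and SAP 6.4.1, 6.6, 6.7 and 7.1 for a special-interest category, a standard MedDRA query, a custom term list or a combined row. None appears. SAP 6.1.1 and 7.1 refer to separate table specifications, which are not among the documents.

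**2. Can the count be recovered from the planned rows?** No. Each row counts men with that term. If three related rows each show 2/30, the number of distinct men lies between the largest row and the sum of the rows:

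- minimum = 2 (the same two men in every row)
- maximum = 2 + 2 + 2 = 6 (no overlap)

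As proportions, that is anything from 6.7% to 20%. The system-organ-class row does not settle it either. If the related terms fall in different classes, no single class row holds them all. If they share a class, its row also includes whatever else is coded there. The documents do not give the coding, so I rely on neither case.

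**3. How much does splitting hide?** Inputs: n = 30 per arm (Protocol 6.1). Assumptions, not document figures: true rate p in one arm, each affected man having one event, and events split evenly over four terms. The yardstick is a row showing 2 or more men.

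- Grouped count: 1 − (1−p)^30 − 30·p·(1−p)^29
- One given row: the same formula with p/4 in place of p
- At least one of the four rows: 1 − Σ(k=0..4) C(4,k)·[30!/(30−k)!]·(p/4)^k·(1−p)^(30−k)

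At p = 0.10:

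- grouped: 1 − 0.042 − 0.141 = 0.82
- given row: 1 − 0.468 − 0.360 = 0.17
- at least one of four rows: 1 − (0.042 + 0.141 + 0.171 + 0.088 + 0.017) = 0.54

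| Assumed true rate | A given row ≥2 | At least one of four rows ≥2 | Grouped count ≥2 |
|---|---|---|---|
| 1% | 0.3% | 1% | 4% |
| 2% | 1% | 4% | 12% |
| 3% | 2% | 8% | 23% |
| 5% | 5% | 20% | 45% |
| 10% | 17% | 54% | 82% |
| 20% | 45% | 92% | 99% |

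**A worked display, again with assumed counts.** Suppose 6 of 30 men on a dose and 0 of 30 on placebo each have one event, split evenly over three terms. Each row reads 2/30 against 0/30 (exact 95% CI for 2/30: 0.8% to 22.1%; Fisher two-sided p = 0.49). The grouped row reads 6/30 against 0/30 (7.7% to 38.6%; p = 0.024). The SAP plans no safety test; the p-values only show how differently the two displays read.

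**The case against.** Several points on the other side are sound and limit what can be claimed.

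- **Events are counted by arm.** A reader might infer that these harms are not counted by arm at all. SAP 6.4.1 contradicts that: every preferred term is tabulated by treatment group, with subjects and events. Only the combined count is missing.
- **Protocol 3.2 does not name thromboembolism.** It names breast and cardiovascular effects, and for diethylstilbestrol. The thrombosis concern has to be taken from Protocol 6.2.2, 8.10 and 9.3.4.1 and SAP 6.8, none of which calls it an estrogen effect.
- **The 100 mg decision does not turn on these tables.** It is tempting to say that split rows endanger the decision to open Stage 2. Safety at that point is reviewed blinded (Protocol 2.0 and 7.2.3, SAP 6.7), so a by-arm table could not inform it in either form.
- **Other safeguards exist.** Serious events are reported within 24 hours, the Safety Review Team meets at least monthly, and listings sorted by subject show a man with two events as one man. A cluster of thrombotic cases would probably be noticed during the trial. These safeguards do not supply a prespecified comparison for the final report.
- **The sample size limits both displays.** Even a grouped 3/30 against 0/30 gives a Fisher two-sided p of 0.24. With no events in 30 men, the one-sided 95% upper limit is still 1 − 0.05^(1/30) = 9.5% (7.2% with 40). At true rates of 1–3% grouping rarely helps. This stands.
- **The undefined reporting category is a separate matter.** Protocol 8.13.4 says "SAEs and events of clinical interest must be reported to the Sponsor (or designee) within 24 hours" without defining the second category. A reader might infer that it means thromboembolic events. The documents do not say so: Protocol 7.2.3 reports liver-test elevations in dogs and Protocol 8.11 has a liver stopping rule, so that reading could be too narrow.
- **The table specifications were not seen.** They may already contain a grouped table.

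**Conclusion.** The point holds as a gap in prespecification. In the documents available, no planned output gives the number of men per arm with at least one thromboembolic or ischaemic event, or with at least one breast event, and the planned rows cannot be combined to give it. The case is stronger for the thromboembolic and ischaemic group. Breast terms may well sit together in one class, though that class row would not be specific to them.

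The gain is largest at moderate rates: 45% against 20% at a true rate of 5%, and 82% against 54% at 10%. It narrows at 20% (99% against 92%) and is of little use at 1–3%. These figures depend on the assumed rates, the even four-way split, one event per affected man and the threshold of two. None of these comes from the documents.

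The benefit is to the final assessment of the safety objective (Protocol 4.4). No efficacy conclusion is affected. This is a worthwhile and inexpensive improvement to the stated method, not an error in a result.

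**What to change.** In SAP 6.4.1, fix two MedDRA term lists before the Week 6 unblinding:

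1. venous and arterial thromboembolic and ischaemic events;
2. breast events.

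For each group, report by arm the number and percentage of men with at least one event, the exact 95% confidence interval, and the difference from placebo. Use each stage's own placebo arm, since SAP 3 and 7.1 keep the two placebo groups apart. Keep the existing preferred-term rows beside the grouped rows. For the blinded Stage 1 safety review, show only the count pooled across arms. If the table specifications already contain this, move the definition into the SAP.

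Cost: two term lists and one table, from adverse events that SAP 6.1.1 already has coded in MedDRA; no new data collection. The drawback is that a grouped count mixes events of different gravity, which is why the single-term rows stay.
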